5.1.3 Fluorescence Endpoints

Specimen-to-background (SBR) ratios will also be calculated using white light and NIR images of both SOC and pegsitanine guided specimens. SBRs will be calculated using *ex situ* images of collected specimens. The equation for calculating SBR is listed below.

$$SBR = \frac{\text{Mean Fluorescence Intensity (Specimen)}}{\text{Mean Fluorescence Intensity (Normal Tissue)}}$$

Note: tumor-to-background (TBR) ratios are equivalent to SBR, but only relevant for specimens with tumors.

5.2 Safety Endpoints

- TEAE incidence, severity, and relationship to study drug
- Physical examination results
- Vital signs results
- ECG results
- Clinical laboratory values (hematology and serum chemistry)

6. ANALYSIS POPULATIONS

6.1 The Safety Population

All patients who receive at least one dose of pegasitacianine.

6.2 The Intent-to-Treat (ITT) Population

Identical to the Safety Population.

6.3 The Efficacy Population

All patients who receive >75% intended dose of pegasitacianine, had a minimum of one (1) image collected during their procedure and had the opportunity for post-SOC evaluation of the thoracic cavity.

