Sample Size	
N=40
 
Up to 40 patients will be enrolled in this study. No set allocation of patients to Part 1 and Part 2 will be implemented, rather Part 2 will be opened at the discretion of the sponsor following the demonstration of satisfactory pegsitacianine sensitivity and specificity values of 70% or greater in Part 1. The sponsor reserves the right to perform an interim analysis following early enrollment (i.e., <math>n \leq 10</math> patients) to determine the feasibility and benefit of pegsitacianine as an adjunct to standard of care lung malignancy resection.

Statistical Analysis	
The quotient of patients with a CSE over the total number of patients undergoing surgery who received any dose of the study drug, and had sufficient imaging data (minimum of 1 collected image). Sensitivity and specificity will be determined at the specimen level based on correlated fluorescence status and pathological outcome.
 
Pegsitacianine performance data will be evaluated in toto, as well as separately if Part 2 of the study is opened to enrollment. Part 1 and Part 2 data will be evaluated independently to assess performance when using different imaging systems within their respective procedure (i.e., minimally invasive vs. open).

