### **9.2 Populations**

All subjects who receive any dose of the study drug will be included in the intent to treat population. The efficacy population will consist of all subjects who receive pegasitacianine and have had a minimum of one (1) image collected during their procedure. The safety population will include all subjects who were administered pegasitacianine whether it be a full or partial dose.

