1. INTRODUCTION

This Statistical Analysis Plan covers the statistical analysis and reporting for the protocol ON-1005 version 02 dated 25JAN2022. A detailed list of tables, listings and figures (TLFs) will be supplied in a separate, version-controlled document.

In case of discrepancies between the SAP and the protocol, the SAP will overrule the protocol with respect to analyses and reporting. Any deviations from the protocol will be documented at the end of this document.

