8. DEVIATIONS FROM ANALYSIS AS DESCRIBED IN THE PROTOCOL

No deviations from the protocol are planned.

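### SAP 6.3 narrows the protocol's efficacy population, SAP 8 says nothing has changed, and no specified output shows the effect on the primary rate

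*SAP*

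**What the plan says.** **Protocol.** Section 9.2 admits to the efficacy population all subjects who receive the agent and "have had a minimum of one (1) image collected during their procedure". It sets no dose threshold. Partial dosing was foreseen, because the same section counts a subject for safety "whether it be a full or partial dose". The Statistical Analysis entry of the Protocol Summary gives the CSE denominator in matching terms: patients undergoing surgery who "received any dose of the study drug, and had sufficient imaging data (minimum of 1 collected image". The revision history says that version 2 updated the analysis populations, and version 2 is the version that the SAP covers.

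**SAP.** Section 6.3 defines the efficacy population as "All patients who receive >75% intended dose of pegasitacianine, had a minimum of one (1) image collected during their procedure", and further requires that they "had the opportunity for post-SOC evaluation of the thoracic cavity". Section 1 says that in case of a discrepancy "the SAP will overrule the protocol with respect to analyses and reporting". It then promises: "Any deviations from the protocol will be documented at the end of this document". Section 8, at that place, reads "No deviations from the protocol are planned".

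SAP 7.10 puts imaging on the Efficacy population. Sections 7.10.1 (CSE responders, with Clopper-Pearson intervals) and 7.10.2 (specimen-level sensitivity, specificity, PPV and NPV) name no population of their own. SAP 7.1 sends changes that may affect the primary conclusions to a protocol amendment and other changes to the clinical study report, and promises an explanation of deviations.

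**The concern.** The denominator of the primary endpoint has changed between two documents that are meant to agree, and the section kept for such changes says there are none. Someone relying on SAP 8 would take the reported CSE rate to be the one the protocol describes.

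The dose condition is at least a number. The cavity condition is not: neither document says what counts as having had the opportunity, or which data item decides it. The study is open-label, so entry to the primary denominator could be judged when the patient's CSE status is already known. A denominator in that position should be traceable to a rule fixed beforehand.

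The same set, by the same inference, carries the specimen-level metrics.

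**Working it through.** **1. The definitions side by side**

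| Condition | Protocol 9.2 and Summary | SAP 6.3 |
|---|---|---|
| Dose | any | more than 75% of intended |
| Images | at least 1 | at least 1 |
| Post-SOC cavity evaluation | not required | opportunity required |
| Definition of opportunity | not applicable | none given |

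The SAP set lies inside the Protocol 9.2 set, which lies inside the Safety population. SAP 6.3 can therefore only remove patients from the protocol's denominator.

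**2. Which definition operates, and on what**

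The precedence clause in SAP 1 makes SAP 6.3 operative. SAP 7.10 speaks of imaging and 7.10.1 is silent, so it is an inference that the any-CSE rate uses the 6.3 set. It is the natural reading, since no other population is named.

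**3. Can a responder be excluded?**

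Under SAP 5.1.1 any one CSE makes a responder. Two types arise during SOC surgery, before the cavity is evaluated: localization of a primary tumor that SOC approaches missed, and an SOC sample that is tumor-negative and does not fluoresce. A patient whose cavity was never evaluated can have either, so exclusions may come from responders, non-responders or both.

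**4. What the specified outputs show**

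- SAP 7.7: number and percentage of enrolled patients in each population.
- SAP 7.9.4: dose administered and dose interruptions, summarized and listed.
- SAP 7.9.5, Safety population: items related to three CSE types (primary tumors identified by NIR, further areas confirmed as cancer after SOC, and non-fluorescent tumor-negative SOC specimens).
- SAP 7.10.1: a listing of CSEs by patient, population not stated.

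None of these is the proportion with any CSE and its exact interval on the Protocol 9.2 population. The 7.9.5 items cannot be added to give it, because one patient may have several CSE types.

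**5. Illustration of size**

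The plan has no figure to reproduce: it states no expected CSE rate, no expected number of exclusions, and no formula behind the 40 subjects. The inputs below are assumptions, apart from N = 40 (Protocol 9.1), all of whom are taken to qualify under Protocol 9.2.

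With x responders among N, removing k patients of whom r are responders gives (x − r)/(N − k), with r from 0 to k. The Clopper-Pearson limits for x of n are the 0.025 quantile of Beta(x, n − x + 1) and the 0.975 quantile of Beta(x + 1, n − x).

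| Assumed case | Rate | 95% CI |
|---|---|---|
| x = 20, none removed: 20/40 | 50.0% | 33.8 to 66.2 |
| two responders removed: 18/38 | 47.4% | 31.0 to 64.2 |
| two non-responders removed: 20/38 | 52.6% | 35.8 to 69.0 |
| x = 12, none removed: 12/40 | 30.0% | 16.6 to 46.5 |
| two responders removed: 10/38 | 26.3% | 13.4 to 43.1 |
| two non-responders removed: 12/38 | 31.6% | 17.5 to 48.7 |

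At 20/40 the shift is 2.6 points either way, against a half-width of (66.2 − 33.8)/2 = 16.2 points. If one of the two removed is a responder, 19/38 = 50.0% and nothing moves.

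**The case against.** The strongest reply is that this is a documentation slip in a pilot. Protocol 9.1 says the study is not powered for hypothesis testing, and the CSE rate has no success threshold. SAP 6.3 states its conditions openly, and the outputs in SAP 7.7, 7.9.4, 7.9.5 and 7.10.1 let a careful reader see how many patients drop out and recover part of the comparison. All of that stands, and it limits the weight of the point. It does not make SAP 8 correct, and it does not supply the missing rate.

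Several stronger readings are tempting, but the documents do not support them.

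- **That the SAP 6.3 set is wrong and the protocol set must be the main one.** The choice is a trade-off. A benign SOC sample that does not fluoresce counts as a CSE, so a patient given little agent could become a responder for that reason alone.
- **That the change was made to improve the result.** SAP 3.1 notes that Part 2 was not opened, so the text was settled after some trial decisions were known. That strengthens the case for declaring the change but does not show that data drove it.
- **That no output or record exists anywhere.** The list of tables, listings and figures is a separate document, and the eCRF and Imaging Workbook were not available. Only the protocol and SAP can be said to lack the rate and the criterion.
- **That Protocol 4.3 gives an exclusion rate.** One of 17 dosed healthy volunteers discontinued the infusion, but that subject also withdrew consent and the share of the dose received is not stated. A trial patient doing the same might have no image and so fail the protocol's definition too.

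**Conclusion.** SAP 8 is wrong as written. SAP 6.3 adds two conditions to the protocol's efficacy population, one of them undefined, and the SAP breaks its own promise to document such a change. By inference from SAP 7.10, the primary any-CSE rate and the diagnostic metrics rest on the narrower set. Neither the protocol nor the SAP specifies the any-CSE proportion with its exact interval on the Protocol 9.2 population.

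Direction and size are unknown, and the effect may be zero. The illustrated shifts depend on assumed response rates and on two assumed exclusions, and each extreme requires both excluded patients to be of the same kind. They lie well inside the wide intervals that 40 patients give. The point should be fixed because the primary denominator is affected and the remedy is cheap. It does not show that the planned estimate is biased.

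**What to change.** 1. Replace the sentence in SAP 8 with the population change and its rationale. Decide which SAP 7.1 route applies, protocol amendment or clinical study report, and record the decision.
2. Name the analysis population in SAP 7.10.1 and 7.10.2 and state in advance which one is the main one. As a supporting analysis, report the any-CSE rate with its exact interval, and the specimen-level metrics, on the Protocol 9.2 population.
3. Tie the opportunity for cavity evaluation to a recorded item that does not depend on CSE status. List each excluded patient with the reason and CSE status.

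The cost is SAP wording, one extra table and one listing. The drawback is that two CSE rates will be in view and may differ, which is why the main one has to be named beforehand.

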7. ANALYTICAL PLAN AND STATISTICAL METHODS

7.1 General Considerations

All computations for statistical analyses will be performed using SAS® software, Version 9.4 or later. All SAS programs used in the production of statistical summary outputs will be validated with independent programming prior to finalization. In addition, all program outputs will be independently reviewed. The validation process will be used to confirm that all data manipulations and calculations were accurately done. Once validation is complete, a senior

statistical reviewer will perform a final review of the documents to ensure the accuracy and consistency with this plan and consistency within tables. Upon completion of validation and quality review procedures, all documentation will be collected and filed by the project statistician or designee.

If necessary, the statistical analytical plan and statistical methods section may be updated before the database lock. Any changes in statistical methods that may have an impact on the primary conclusions drawn from this clinical trial will be described in an amendment to the protocol. All other changes in the statistical plan will be described in the clinical study report (CSR). An explanation will be provided for deviations from the planned analysis.

7.2 Reporting Conventions

The following conventions will be applied to all data presentations and analyses:

- Continuous variables will generally be summarized by the number of patients with missing and non-missing values, mean, standard deviation, median, Q1 (quartile 1), Q3 (quartile 3), minimum, and maximum.
- Categorical variables will be summarized by the number and percentage of patients within each category. If not specified otherwise, the number of patients with non-missing values will be the denominator for percentage calculations. The number of patients with missing values will be presented.
- Confidence intervals will be reported as two sided at the 95% level.
- All mean and median values will be formatted to one more decimal place than the measured value.
- Standard deviation values will be formatted to two more decimal places than the measured value.
- Minimum and maximum values will be presented with the same number of decimal places as the measured value.
- The number and percent of responses will be presented in the form XX (XX %), where the percentage is in parentheses. Percentages will be rounded to the nearest percent. In

the case of a frequency of zero, the frequency and percentage will be presented as 0 rather than 0 (0%).

- Date variables will be formatted as DDMMYY for presentation

All the analyses will be run displaying the results from Part 1. All rates will be summarized using counts and percentages.

7.3 Definition of Baseline

Baseline is defined as the measurement closest to, but prior to, the administration of study drug. No reassignment of visits will be conducted.

7.4 Handling of Dropouts and Missing, Unused and Spurious Data

All data will be analyzed.

No imputation of missing data will be performed, and analyses will use the observed cases only.

Formal outlier testing will not be performed. Data identified as potential outliers after review will be reviewed to determine whether they are spurious.

Spurious data are data determined to be incorrect upon review of site documents. If data is deemed to be spurious, the spurious data and the reason for it being spurious will be documented by the Sponsor in a Note-to-file. Data identified as spurious will be treated as missing unless they can be definitively corrected. If spurious data is identified, sensitivity analysis may be performed to assess the potential impact of any missing data or outliers on trial results by including the spurious data.

7.4.1 Dates

Imputation of missing or partial dates is not expected, but if a complete date is required for calculations, the following algorithms will be applied:

- For the start date:
 - If year, month, and day are missing then use the minimum of the patient's first visit date or the consent date.
 - If either only month or month and day are missing then use January 1.

- If only day is missing, impute the first day of the month.
- For the end date:
 - If year, month, and day are missing then use the patient's last visit date.
 - If either only month or month and day are missing then use December 31.
 - If only day is missing then use the last day of the month.
 - Do not expand the record past the patient's last visit.
 - The original missing or partial date, the imputed complete date, and the indicator variable that indicates which dates were imputed will be retained in the database.

7.5 Adjustment for Multiplicity

There are no planned adjustments for multiple endpoints or analyses.

7.6 Adjustment for Multiple Centers

Differences between study centers will not be incorporated into the statistical analyses for this study. There are no plans to analyze data within centers.

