## PROTOCOL SUMMARY

Protocol Number	ON-1005
Title of Trial	A Phase 2, single-dose, open-label study to evaluate diagnostic performance and safety of pegsitacianine, an intraoperative fluorescence imaging agent, for the detection of lung malignancies in patients undergoing routine surgery
Phase of Clinical Trial	Phase 2
Indications	Pegsitacianine is indicated as an imaging agent for intraoperative detection of lung malignancies in the thoracic cavity during routine surgical resection. Pegsitacianine is administered as a single dose prior to surgery.
Study Centers	up to 5 centers
Trial Objectives	
Primary Objective: The primary objective of this study is to determine if administration of pegsitacianine ( mg/kg) results in a clinically significant event at the level of the patient.
 
Examples of clinically significant events include:
 
 
1. The detection of disease that cannot be detected using standard procedures
 
2. The detection of synchronous lesions
 
3. The detection of positive surgical margins following primary tumor resection
 
4. Tumor-negative standard of care (SOC) biopsy
 
 
Secondary Objectives: Key secondary objectives are to evaluate the safety and toxicity of pegsitacianine. Additionally, the sensitivity, specificity, negative predictive values, and positive predictive values of the imaging agent will be calculated at the level of the individual specimens, including lymph nodes.

Background	Pegsitacianine is a novel intraoperative nanoparticle-based fluorescence imaging agent that was evaluated during the first-in-human Phase 1 study (ON-1001). ON-1001 was completed in the Netherlands in patients with solid cancers undergoing surgical excision of their tumors. An additional Phase 1 study (ON-1004) evaluating the pharmacokinetics in a healthy volunteer population has also been completed. Pegsitacianine was further evaluated in a completed Phase 2 study (ON-1002) in solid tumors. Pegsitacianine fluorescence is quenched when exposed to normal physiological pH but becomes activated following micellar disassembly in the acidic tumor microenvironment. Pegsitacianine was demonstrated to be well tolerated and showed no dose-limiting toxicities (DLT).

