Collected surgical specimens will be documented by the clinical research coordinator in the Imaging Workbook as called out by the surgeon. The fluorescence status of each specimen will similarly be assessed and called out by the surgeon (fluorescent or not fluorescent). All samples will be sent to pathology for routine analysis. To determine the performance metrics of pegsitacianine, the fluorescence status of each specimen will be correlated to the final pathology and results will be tabulated.

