#### 6.5 Training

Extensive training will be provided to all study staff. Initial training will occur at the Site Initiation Visit, followed by on-site training that will take place during the initial surgical procedures with Sponsor Representatives present in the operating room during the procedures. Sponsor Representatives will ensure all study personnel are adequately trained and follow identical procedures to preserve the integrity of the collected data without providing input on the selection of specimens or their fluorescent status, these tasks are the sole responsibility of the operating surgeon. Additional retraining may take place if necessary throughout the course of the study. Training will include a review of protocol procedures, NIR camera operating instructions, documentation of specimens and their fluorescence status, and upload of source documentation. All training will be documented and stored within the Trial Master File.

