### **9.1 Sample Size**

The sample size for this study will be 40 subjects. This sample size is based on historical experience with similar pilot studies with the goal of informing power calculations for future studies. This study is not formally powered for hypothesis testing. A sample size of 40 subjects will be sufficient for developing further understanding of the endpoints described herein. Sample size calculations account for non-evaluable and drop-out patients.

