## **14. APPENDIX 2: FDA-CLEARED NIR IMAGING DEVICES**

**NOTE:** this list is not comprehensive and does not restrict the use of other FDA-cleared imaging device from use in this trial.

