4. SAMPLE SIZE AND POWER CALCULATION

The sample size for this study will be 40 subjects. This sample size is based on historical experience with the proposed analysis. A sample size of 40 subjects will be sufficient for meeting the endpoints described herein.

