7.10.3.3 Camera System Analysis

An analysis on diagnostic results by camera system will be performed. 2x2 incidence tables comparing the true/false negative/positive results will be constructed for each camera system, and compared via the Breslow-Day test to assess if there is any effect of camera system on diagnostic results (e.g. to test if the common odds-ratio of each incidence table is equivalent across camera types). A summary including the diagnostic true/false negative/positive numbers and rates for each camera system, sensitivity, specificity, and p-value of this analysis will be provided.

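### The exploratory camera comparison in SAP 7.10.3.3 pools specimens over centers, so if camera use follows center it cannot separate camera from center or surgeon

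*SAP*

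**What the plan says.** - **Center.** SAP 7.6: "Differences between study centers will not be incorporated into the statistical analyses for this study. There are no plans to analyze data within centers".
- **Camera.** SAP 7.10.3.3 builds one 2x2 table of fluorescence against pathology per camera system and applies the Breslow-Day test "to assess if there is any effect of camera system on diagnostic results". It names no center or surgeon term. SAP Table 1 lists the camera effect as an exploratory objective.
- **Who makes the call.** Protocol 3.1 has the surgeon declare each specimen fluorescent or not. On selecting specimens and calling their fluorescence, Protocol 6.5 says "these tasks are the sole responsibility of the operating surgeon". Neither document describes a second or central reader of that call. SAP 7.10.3.2 takes any fluorescence as positive.
- **Which devices.** Protocol 3.1 requires an appropriate FDA-cleared device. Protocol Appendix 2 gives examples and says its list "does not restrict the use of other FDA-cleared imaging device from use in this trial".
- **Scale.** The Protocol Summary allows "up to 5 centers". SAP section 4: "The sample size for this study will be 40 subjects". Protocol 9.1: "This study is not formally powered for hypothesis testing".
- **Listings.** The SAP plans patient-level surgery details including camera (7.9.5), CSEs by patient (7.10.1.1), and results by subject and specimen (7.10.2.1). None of these names a center or surgeon column, and 7.10.2.1 names no camera column.

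**The concern.** The fluorescence result is a product of the camera and of the surgeon reading it, with no numeric cut-off to bring surgeons into line. A center may well rely mainly on the NIR system it already owns. If so, the tables for different cameras are also tables for different surgeons, patients and specimen handling. The SAP would then attach a p-value for a camera effect to a contrast that mixes all of these, having left out the factor most likely to travel with camera.

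What is at stake is what the trial can say about cameras. An operator difference could be reported as a device difference, or could mask one. There is a lesser descriptive gap as well. The CSE responder rate depends partly on surgeon practice, because a responder needs only one SOC specimen that is pathology-negative and did not fluoresce *ex situ* (SAP 5.1.1). No planned table would show whether one center drives that rate. Protocol 9.1 wants this pilot to inform the power calculations of later studies, for which between-center spread is useful.

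**Working it through.** **No figure to reproduce.** The 40 subjects rest on historical experience, and no alpha is stated for the camera test. The check is of what the comparison can identify, with illustrations whose inputs are assumptions.

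**1. Identification.** For camera k, the pooled log diagnostic odds ratio (DOR) reflects a common level, a camera effect and the effects of the centers that used camera k. If each center used only one camera, the data give only the sum of the last two. Breslow-Day tests whether DORs are equal across cameras, so it tests that sum.

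**2. Two identical cameras, different surgeons** (assumed: 40 tumor and 60 non-tumor specimens per camera; DOR = TP x TN / (FN x FP)).

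- *Accuracy differs.* Sensitivity/specificity 0.90/0.85 gives TP 36, FN 4, TN 51, FP 9: DOR = 36 x 51 / (4 x 9) = 51.0. With 0.70/0.65, TP 28, FN 12, TN 39, FP 21: DOR = 28 x 39 / (12 x 21) = 4.33. Breslow-Day p = 0.001, which would be read as a camera effect.
- *Only the calling threshold differs.* With 0.90/0.60, DOR = 36 x 36 / (4 x 24) = 13.5. With 0.60/0.90, DOR = 24 x 54 / (16 x 6) = 13.5. Breslow-Day p = 1.0. The test misses a 30-point difference in both sensitivity and specificity. The by-camera rates would show it, labeled as camera.

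**3. How often a false camera effect appears.** Simulation with no true camera effect, 4,000 runs per setting. Assumptions: 5 centers x 8 subjects x 5 specimens, 40% tumor-positive, baseline sensitivity 0.80 and specificity 0.75, two cameras, alpha 0.05, no within-subject correlation. Runs with an empty cell were left out. Center effects on log DOR are normal and split equally between sensitivity and specificity.

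| Between-center SD of log DOR | Significant, one camera per center (2 centers vs 3) |
|---|---|
| 0 | 4.9% |
| 0.5 | 10.4% |
| 1.0 | 22.0% |
| 1.5 | 32.9% |
| 2.0 | 44.2% |

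When both cameras were used evenly in every center, the rate stayed at 3.6% to 5.5% over the same range.

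To read the scale: baseline odds are 0.80/0.20 = 4 for sensitivity and 0.75/0.25 = 3 for specificity. At SD 1.0, a center one SD above average multiplies each by e^0.5 = 1.649, giving 6.595/7.595 = 0.87 and 4.946/5.946 = 0.83. One SD below multiplies by 0.6065, giving 2.426/3.426 = 0.71 and 1.820/2.820 = 0.65.

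**4. What by-center tables can show.** An even split gives 40/5 = 8 patients per center. The exact 95% interval for 4/8 is 15.7% to 84.3%; for 20/40 it is 33.8% to 66.2%. Single-center rates can be displayed but not tested.

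**The case against.** The best reply is that this is an exploratory analysis in a single-arm pilot not powered for testing, and that the premise is not in the documents, which do not say which camera any center used. Both parts are true. The first limits the severity; the second makes this a risk, not a demonstrated bias. Where the documents do tie imaging systems to something, it is the procedure: the Statistical Analysis entry of the Protocol Summary expects systems to differ between minimally invasive and open surgery. Part 1 mixes VATS and robotic cases, so approach is a second candidate confounder and belongs in the same check.

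A reader might infer more than the text supports:

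- *That camera choice is unrestricted.* Devices must be appropriate and FDA-cleared; only the list of examples is open.
- *That SAP 7.6 forbids any output by center.* It rules out incorporating center differences and says no within-center analysis is planned. Protocol section 9 allows additional analyses, and SAP 7.10.3.4 allows post-hoc covariates.
- *That operator effects are wholly hidden.* The specimen listing sets fluorescence status beside measured intensity, and the ROC analysis uses intensity ratios, not the surgeon's call. A manual tally is possible if subject identifiers carry the site, which the SAP does not state. The supportable claim is that no planned summary shows it.
- *That early cases attended by sponsor representatives need separate analysis.* Protocol 6.5 says representatives give no input on specimen selection or fluorescence status.
- *That a distorted pooled specificity could open Part 2 wrongly.* SAP 3.1 records that Part 2 was not opened.

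It is also fair that a pure threshold difference need not move the Breslow-Day p-value. That weakens one route to a false positive but does not make the comparison interpretable.

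**Conclusion.** The point holds as a conditional one. If camera use largely follows center, the SAP 7.10.3.3 comparison cannot separate camera from center or surgeon, and nothing in the planned summaries would alert the reader. Under the stated simulation assumptions, the false-positive rate rises from 4.9% to between 10.4% and 44.2% as the between-center SD of log DOR goes from 0.5 to 2.0. These rates illustrate the mechanism; they do not estimate what this trial would show, since neither the camera allocation nor the between-center variation is documented.

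The consequence is confined to the exploratory camera objective and to the missing descriptive view by center. The documents do not support a claim that the primary CSE rate or the pooled sensitivity and specificity are invalid. The change should be made because it is cheap and determines whether the trial can say anything about cameras.

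**What to change.** In SAP 7.10.3.3:

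- Add cross-tabulations of camera by center and of camera by VATS/robotic approach, in patients and specimens, to be read before the comparison.
- Where centers used more than one system, stratify the camera comparison by center. Breslow-Day already uses camera as its stratum, so the form needs stating. One option is a Mantel-Haenszel comparison of cameras with center as stratum, done separately in tumor-positive and tumor-negative specimens; this would also pick up a threshold shift.
- If camera is nested in center, report by-camera counts, sensitivity and specificity descriptively, labeled *camera/center, not separable*, with no p-value.

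In SAP 7.6, state that CSE responder counts and true/false positive/negative counts will be tabulated by center, descriptively and without testing. In SAP 7.10.2.1, add center and camera to the subject/specimen listing, and surgeon if recorded.

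**Cost.** SAP text, a few tables and extra listing columns, with no new patients or procedures. Camera system is already summarized under SAP 7.9.5; the documents do not confirm that surgeon identity is captured. SAP 7.1 permits updates before database lock. The drawbacks are very small cells in the by-center tables and the possible loss of the camera p-value.
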